#### 3.2.2 Alternative hypothesis (H1)

PRO-185 ophthalmic solution is safe and tolerable for ophthalmic use, as it did not present any of the following AEs in more than 10% of subjects: increased IOP (>5 mmHg), changes in HR (>15 bpm), increased systemic blood pressure (>15 mmHg in SBP or >10 mmHg in DBP), pharmacological mydriasis, or grade 3 and 4 conjunctival hyperemia.

$$H_1 = p - p_0 > \delta$$

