10.1.2 Size calculation

PRO-185 ophthalmic solution is expected to present in less than 20% of subjects any of the following AEs: increased IOP (>5 mmHg), heart rate changes (>15 bpm), increased systemic blood pressure (>15 mmHg in SBP or >10 mmHg in DBP), pharmacological mydriasis or grade 3 and 4 conjunctival hyperemia, 20 minutes after its application with respect to its initial value.

The sample size was calculated using the equation for a non-superiority proportion [53]. This equation is useful for non-inferiority/superiority tests, if we want to test whether a proportion (p) is not superior to a reference value, p_0 (20% in this case). The idea is that statistically significant differences between the proportion and the reference value cannot be of interest unless the difference is greater than a threshold δ (10% in this case). This type of calculation is useful in clinical studies where the value of δ is chosen based on clinical judgment and knowledge of the subject.

The hypothesis test is:

$$H_0: p - p_0 \leq \delta$$

$$H_1: p - p_0 > \delta$$

Equations

The calculation to estimate the sample size and power was performed using an online tool and following the equations [53]:

$$18 = p(1 - 0.2) \left(\frac{1.96 + z_{1-\beta}}{p - 0.2 - 0.1} \right)^2$$

$$1 - \beta = \Phi(z - 1.96) + \Phi(-z - 1.96), z = \frac{p - 0.2 - 0.1}{\sqrt{\frac{p(1 - 0.2)}{18}}}$$

Where:

n is the sample size (18)

p₀ is the reference value (0.20)

Φ is the function of the standard normal distribution

Φ⁻¹ is the function of the standard normal distribution

α is the Type I error (1.96)

β is the Type II error, which means that, 1-β (1-0.8) is the power

δ is the test margin (0.10)

According to the previous calculation, 18 subjects are estimated, increasing the calculation by 20% considering possible losses, 22 subjects are estimated to contribute OA to the study. This calculation is in accordance with the average number of subjects used in the clinical studies reviewed in the search performed in PubMed and Web of Science (24 subjects), where the incidence of adverse events was similar to that expected in this study.

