### 3.2 Study Hypothesis

#### 3.2.1 Null hypothesis (H0)

PRO-185 ophthalmic solution is not safe and tolerable for ophthalmic use because more than 10% of subjects experienced any of the following AEs: increased IOP (>5 mmHg), changes in HR (>15 bpm), increased systemic blood pressure (>15 mmHg SBP or >10 mmHg DBP), pharmacological mydriasis, or grade 3 and 4 conjunctival hyperemia.

$$H_0 = p - p_0 \leq \delta$$

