## 4. Sample Size Calculation

The sample size calculation was based on the study's primary objective: to evaluate the safety and tolerability of PRO-185 ophthalmic solution (naphazoline hydrochloride 0.03%) in ophthalmologically healthy subjects. To meet the study's primary objective, 22 subjects are estimated to contribute OA to the study.

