## 6.1 Population analysis

Statistical analysis will be presented to give an overall summary of the subjects entered into the study and an overview of the safety and tolerability of its results. The data provided by the research site will be summarized for this purpose, according to their nature. The Shapiro-Wilk test will be performed to determine whether the quantitative data are normally distributed.

The results of the quantitative variables will be presented in measures of central tendency: mean, standard deviation, maximum and minimum. The changes in pupil diameter, BCVA, and in the Body temperature will be expressed as continuous variables. Changes in IOP, HR, systemic blood pressure, TVL, and TF will be expressed as discrete variables.

The results of nominal and ordinal qualitative variables will be presented as frequencies, proportions, and/or percentages. For these, 2 x 2 frequency tables will be constructed. All percentages will be presented with one decimal place.

The level of difference considered significant will be an alpha ( $\alpha$ ) of 0.05 or less. The triangulation between the type of variable and the measurements is shown in **Table 3**.

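### Read in words, SAP 3.2 claims an event rate not above 10%, but 22 subjects cannot exclude 10% even with zero events; the size was derived for excluding 30%

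*SAP*

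**What the plan says.** SAP 3.2.1 gives the null in words: "PRO-185 ophthalmic solution is not safe and tolerable for ophthalmic use because more than 10% of subjects experienced any of the following AEs". The events are a rise in intraocular pressure, a change in heart rate, a rise in blood pressure, pharmacological mydriasis, or grade 3 and 4 hyperemia. SAP 3.2.2 gives the alternative: "PRO-185 ophthalmic solution is safe and tolerable for ophthalmic use, as it did not present any of the following AEs in more than 10% of" those treated. The symbols beside these sentences are H0: p − p0 ≤ δ and H1: p − p0 > δ, and SAP 4.2 repeats them.

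On size, SAP 4 says: "To meet the study's primary objective, 22 subjects are estimated to contribute OA to the study". SAP 4.1 and 4.2 take 10% as the adverse event proportion entered and expected, set δ at 10%, and arrive at 18 plus 20% for losses. The SAP gives no value for p0 or for power.

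On the test, SAP 6.1 says "The level of difference considered significant will be an alpha" of 0.05 or less, without stating sidedness. SAP 6.2.1 analyses all dosed subjects. It names Kolmogorov-Smirnov or Mann-Whitney for the quantitative measurements, and Pearson chi-square or Fisher for hyperemia. It names no test of a proportion against 10%.

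Protocol 3.2 uses 20%, places safety in H0, and rejects H0 if any one event type has a frequency above 20%. Protocol 10.1.2 supplies the sizing values that the SAP omits: p0 = 0.20, δ = 0.10, "α is the Type I error (1.96") and "β is the Type II error, which means that, 1-β (1-0.8) is the power".

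**The concern.** In the SAP's words, safety is the alternative, so the data must exclude an event rate above 10%. With about 20 subjects, zero events still leaves an upper confidence limit above 10%. If so, a trial with no events at all would formally end without showing the claim. The practical risk is that the decision is then improvised, most simply by declaring safety whenever the observed rate is 10% or less. That rule has no controlled error rate.

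The 10% also plays two roles. In SAP 4.1 and 4.2 it is the rate expected; in SAP 3.2 it is the limit to be ruled out. A sample size built on the first use need not support the second.

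**Working it through.** **1. Reproduce the planned size.** Inputs: p = 0.10 (SAP 4.1), p0 = 0.20, δ = 0.10 and z = 1.96 (protocol 10.1.2). Power of 80% (z = 0.8416) is how I read the protocol's power entry. With the SAP 4.2 formula:

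n = p(1 − p)[(z_α + z_β)/(p − p0 − δ)]² = 0.10 × 0.90 × [(1.96 + 0.8416)/(0.10 − 0.30)]² = 17.66, rounded up to 18.

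The power at n = 18 is 80.7%. Adding 20% gives 18 × 1.2 = 21.6, hence 22.

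The variance term as printed in the protocol, p(1 − 0.2), gives 15.7, or 16. One-sided 0.05 gives 13.91, or 14. A boundary of 0.20 with p = 0.10 gives 70.64, or 71. Among these, only excluding 30% at a true rate of 10% with z = 1.96 gives 18.

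**2. Test the SAP's wording at its most favourable result, zero events.** The exact one-sided p-value against 10% is 0.9^n. The exact upper limit is 1 − α^(1/n). The score statistic is −0.10/√(0.09/n).

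| | n = 22 | n = 18 |
|---|---|---|
| Exact one-sided p | 0.0985 | 0.150 |
| Score z (one-sided p) | −1.56 (0.059) | −1.41 (0.079) |
| One-sided 95% upper limit | 12.7% | 15.3% |
| One-sided 97.5% upper limit | 15.4% | 18.5% |

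At n = 22 the two-sided exact p is 0.161. Zero is the lowest possible count, so under these tests no data reject the null. Zero events first exclude 10% at n = 29 (0.9^29 = 0.047) for one-sided 0.05, and at n = 36 (0.9^36 = 0.0225) for one-sided 0.025.

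**3. The observed-rate alternative.** An observed rate of 10% or less means at most 2 of 22 (2/22 = 9.1%, 3/22 = 13.6%). The chance of passing is P(X ≤ 2 | 22, 0.10) = 0.62 and P(X ≤ 2 | 22, 0.20) = 0.154.

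**4. Limits that this number of subjects could exclude.** The table gives the largest count whose exact one-sided p is at most 0.05, with the chance of meeting it at a true rate of 10%.

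| n | Against 20%: count (p), pass | Against 30%: count (p), pass |
|---|---|---|
| 22 | 1 (0.048), 34% | 2 (0.021), 62% |
| 21 | 0 (0.009), 11% | 2 (0.027), 65% |
| 20 | 0 (0.012), 12% | 2 (0.036), 68% |
| 19 | 0 (0.014), 14% | 2 (0.046), 70% |
| 18 | 0 (0.018), 15% | 1 (0.014), 45% |

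The counts shift as soon as subjects are lost. One event against 20% gives p = 0.058 at n = 21 and 0.099 at n = 18. Two events against 30% give 0.060 at n = 18.

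**The case against.** The strongest reply is that the SAP never specifies this test. SAP 6.2.1 names no comparison of a proportion with 10%, and the alpha in SAP 6.1 is a general significance level. The hypotheses can be read as statements about what is observed, much as protocol 3.2 decides on a frequency, and then up to 2 of 22 would satisfy the SAP. The printed symbols also place a high event rate in H1, with a boundary of p0 + δ. On that reading the rejection region is not empty: at one-sided 0.05 with 22 subjects it starts at 6, 9 or 11 events for a boundary of 10%, 20% or 30%.

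All of this stands, and it limits the conclusion. A reader might infer that the trial has 0% power against a planned 80%, or that it can never conclude safety. The documents do not support that as a flat statement. The 0% belongs to the verbal hypotheses tested by an exact or score method. The 80% belongs to the protocol's 30% boundary, so the two figures concern different questions.

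A reader might also fear that counting 44 eyes as independent would rescue the claim (0.9^44 = 0.0097). Nothing in the SAP proposes this, the hypotheses are stated in subjects, and heart rate and blood pressure have no per-eye value.

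The reply does not remove the point. SAP 4.2 presents the proportion comparison as the hypothesis test, so the SAP does not present itself as purely descriptive. The observed-rate reading avoids the empty region only by giving up error control. A one-sided mid-p test would just reject at 0 of 22 (0.0985/2 = 0.049), but no document specifies it and it fails at one-sided 0.025. Adopting the protocol's 20% would remove the 10% limit, but would still leave the basis of the sample size and the form of the decision unstated.

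**Conclusion.** The point holds conditionally. If SAP 3.2 is tested as worded, per subject, at alpha 0.05 by an exact or score test, 22 subjects cannot support the claim: the best possible result gives p = 0.098 and excludes only rates above 12.7% (one-sided 95%). If safety is instead declared on the observed rate, the rule passes 62% of the time at a true rate of 10% and 15% at 20%. If the symbols govern, neither figure applies, but the words beside them are then wrong.

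On every reading, the planned size rests on excluding 30% at an expected 10% and does not support a claim of not more than 10%. That reconstruction takes p0 and z from the protocol and 80% as the intended power, since the SAP prints none of these values. SAP 3.2 and 4.2 need to be corrected before analysis.

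**What to change.** Keep 22 subjects.

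- In SAP 3.2 and 4.2, make the words and symbols agree, and align both with protocol 3.2. Remove 10% as a tested limit and label it the expected rate.
- State that n = 18 was sized to exclude 30% at a true rate of 10%, and that 0 of 22 excludes only rates above 12.7% (one-sided 95%).
- Base the conclusion on the exact per-subject upper confidence limit for each event rate, computed on the number actually evaluable. Compare it with one limit prespecified in both documents, and state the confidence level and sidedness. Do not use a fixed event count.
- The sponsor should justify that limit clinically rather than choose it because 22 subjects can pass it. If it is 20% or 30%, print the passing count and power for each n from 18 to 22, as tabulated above.

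This costs no subjects or procedures, but it is not an SAP-only edit. Protocol 3.2 places safety in H0, so a conclusion that rests on an upper limit requires the protocol wording to change at the same time. The claim also becomes less favourable, and the chance of meeting it is modest: at n = 22 and a true rate of 10%, 34% against 20% and 62% against 30%.

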### 3.3 Study Variables

#### 3.3.1 Primary outcome variables

- Intraocular pressure
- Heart rate
- Systemic blood pressure
- Pupillary size
- Conjunctival hyperemia

#### 3.3.2 Secondary outcome variables

- Best corrected visual acuity (BCVA)
- Corneal and conjunctival staining changes with lissamine green (LG)
- Corneal and conjunctival staining changes with fluorescein (TF)
- Incidence of chemosis
- Incidence of adverse events
- Incidence of unexpected adverse events

#### 3.3.3 Exploratory Variables

- Respiratory rate
- Body temperature

### 3.4 Subject's duration in the study/treatment

Up to 11 days, 1 drop 4 times a day in both eyes (OE) for 8 days, see Table 1.

[figure not shown]

Figure 1. Study diagram

Table 1. Study schedule

Procedures	Baseline visit		Visit 1		Visit 2		Final visit Day 10 (+1) Without treatment	
	Day 1		Day 3 (+1)		Day 8			
	Pre-Tx	Post-Tx	Pre-Tx	Post-Tx	Pre-Tx	Post-Tx		
FCI Signature	X							
Medical record	X							
Eligibility criteria	X							
Subject code assignment	X							
Adverse events	X	X	X	X	X	X	X	
Heart rate	X	X	X	X	X	X	X	
Frequency respiratory	X		X		X		X	
Blood pressure	X	X	X	X	X	X	X	
Temperature (°C)	X		X		X		X	
Pregnancy test in urine	X						X	
AVMC	X		X		X		X	
Evaluation of the anterior segment		X		X		X		
Pupillary diameter measurement	X	X	X	X	X	X	X	
Eye stains	X	X	X	X	X	X	X	
Intraocular pressure	X	X	X	X	X	X	X	
Evaluation of the posterior segment	X		X		X		X	
Application of the medicine in visit	X		X		X			
Delivery of material for the subject		X						
Delivery of the medication study		X						
Evaluation of medications concomitants	X		X		X		X	
Evaluation of the adherence			X		X			
Return of the medicine of the study						X		
Withdrawal from the diary of subject						X		

Pre-Tx: pretreatment, indicates the assessments to be performed before administration of the investigational drug. Post-Tx: post-treatment, indicates the evaluations to be performed within 20–40 minutes after administration of the investigational drug. ICF: informed consent form. BCVA: best-corrected visual acuity.

### 3.5 Randomization

As this is an open, non-comparative study, randomization of subjects entering the study is not necessary.

### 3.6 Subject code assignment

After verifying the inclusion/exclusion criteria, eligible subjects will be identified by a number and their initials.

The initials of the subject of study will be obtained starting with the first letter of the name, followed by the first letter of the first surname and the first letter of the second surname, obtaining a maximum of three letters. In case the person has two names or a compound surname, the first letter will always be used.

Example:

to.	[name]	B. [name]
to.	Initials: AMC	b. Initials: JDO

Once the subject has been selected, they will be assigned a number that will identify them throughout the study. This code will consist of eight numbers in the following order from left to right:

- three digits of the molecule under study according to the sponsor's name.
- two digits corresponding to the research center number.
- three digits of the consecutive number assigned to its inclusion in the research center.

Example:

185-01-001

## 4. Sample Size Calculation

The sample size calculation was based on the study's primary objective: to evaluate the safety and tolerability of PRO-185 ophthalmic solution (naphazoline hydrochloride 0.03%) in ophthalmologically healthy subjects. To meet the study's primary objective, 22 subjects are estimated to contribute OA to the study.

### 4.1 Calculation methodology

A search was carried out in the open access search engines PubMed (pubmed.ncbi.nlm.nih.gov) and Web of Science (webofscience.com), finding until May 2021, 102 results in PubMed and 24 in Web of Science that matched the keywords of

Search: "Naphazoline Ophthalmic". The extract was generated from this search, and the integrated database was reviewed to eliminate duplicate matches and filter out those articles that were consistent with the study objective. After reviewing the *abstracts* (available only in 89 articles), 7 articles were selected for full-text review. Of these, 5 articles were selected to make the sample size proposal.

[2, 3, 4, 5], one of them is a review article [6], this was used only as a reference (see [Annex 9.1](#)).

The mean  $\pm$  standard deviation (SD) sample size used in the selected studies was  $24.4 \pm 21.24$  subjects (range 6–60). Considering a 10% proportion in the incidence of AEs, these values were entered into an online tool [7] to estimate the sample size and power, following the specific equations for the calculation [8].

Finally, the calculated value was increased by 20% to account for possible losses.

## 4.2 Proposal

PRO-185 ophthalmic solution is expected to present in less than 10% of subjects any of the following AEs: increased IOP ( $>5$  mmHg), heart rate changes ( $>15$  bpm), increased systemic blood pressure ( $>15$  mmHg in SBP or  $>10$  mmHg in DBP), pharmacological mydriasis or grade 3 and 4 conjunctival hyperemia, 20 minutes after its application with respect to its initial value.

The sample size was calculated using the equation for a non-superiority proportion [8]. This equation is useful for non-inferiority/superiority testing, if we want to test whether a proportion ( $p$ ) is not superior to a reference value,  $p_0$ . The idea is that statistically significant differences between the proportion and the reference value cannot be of interest unless the difference is greater than a threshold  $\delta$  (10% in this case). This type of calculation is useful in clinical studies where the value of  $\delta$  is chosen based on clinical judgment and subject matter expertise (see [Appendix 9.1](#)).

The hypothesis test is:

$$H_0: p - p_0 \leq \delta$$

$$H_1: p - p_0 > \delta$$

Equations

The calculation to estimate the sample size and power was performed using an online tool and following the equations [8]:

$$n = p(1-p) \left( \frac{z_{1-\alpha} + z_{1-\beta}}{p - p_0 - \delta} \right)^2$$

$$1 - \beta = \Phi(z - z_{1-\alpha}) + \Phi(-z - z_{1-\alpha}), z = \frac{p - p_0 - \delta}{\sqrt{\frac{1-p}{n}}}$$

Where:

$n$  is the sample size,

$p_0$  is the reference value,

$\Phi$  is the function of the standard normal distribution,

$\Phi^{-1}$  is the function of the standard normal distribution,

$\alpha$  is the Type I error,

$\beta$  is the Type II error, which means that,  $1-\beta$  is the power, and

$\delta$  is the test margin.

According to the previous calculation, 18 subjects are estimated per treatment arm. Considering potential losses, the estimate increases by 20%. This estimate is consistent with the average number of subjects used in the clinical studies reviewed in the PubMed and Web of Science searches (24 subjects).

## 5. Clinical Data Management

*Clinical* data management (CDM) enables the generation of high-quality, reliable, and statistically valuable data. CDM is the process of collecting, cleaning, and managing subject information in a study in compliance with regulatory standards (21 CFR Part 11, ICH, and GCP guidelines). It encompasses eCRF design, eCRF commenting, database design, *data entry*, *source document verification* (SDV), discrepancy management (queries), medical *coding*, *soft lock*, and *hard lock* [9].

In accordance with roles and responsibilities, multiple users can be created, whose access types to the eCRF can be limited to data entry (principal investigator, PI), medical coding, database design, or quality control (QC) [9, 10]. Discrepancy handling will be performed based on the flow in [Figure 2](#).

The CDM team will include the following roles:

- Data Manager,
- Database designer/programmer,
- Clinical coder (*Medical coder*),
- Clinical data coordinator,
- Quality control, and
- Capturist (*data entry associate*).

[figure not shown]

Figure 2. Discrepancy management (DCF, medical note; CRA, clinical monitor; SEC, self-evident correction) [9]

## 6. Statistical Methodology

The PAE was developed considering the evaluation criteria described in the study protocol.

Statistical analysis will be performed by personnel from Laboratorios Sophia, SA de CV. The SPSS statistical package version 19.0 for Windows (IBM Corporation, Armonk, NY, USA) will be used.

Coding will be performed using consecutive numbers. Data will be collected and organized in an Excel spreadsheet (Microsoft® Office). The data will then be exported to the SPSS package platform.

Variables will be categorized according to their nature (see Table 2). The statistical tests used will follow the corresponding assumptions for nonparametric statistics.

Table 2. Operational Definition of the Variables

Variable	Conceptual Definition	Operational Definition	Type of measurement	Value of reference	Proof statistics
Pressure Intraocular	Tonometry is the objective measurement of IOP, based on the force required to flatten the cornea or the degree of corneal indentation produced by a fixed force.	By means of tonometry Goldmann based on the Imberk-Fick principle.	Quantitative discreet	10 – 21 mmHg	Kolmogorov-Smirnov or U Mann's Whitney*
Heart rate	The pulse is a measurement of the FC, that is, the amount of	For each heartbeat, the left ventricle contracts and expels blood into the heart.	Discrete quantitative	60 – 100 bpm	Kolmogorov-Smirnov or U

Variable	Conceptual Definition	Operational Definition	Type of measurement	Reference value	Statistical test
	times the heart beats per minute.	of the aorta. This forceful expulsion of blood creates a wave that is transmitted to the periphery of the body through the arteries. Measured with a			Mann's Whitney*
		electronic or manual blood pressure monitor.			
Pressure systemic arterial	It is the force exerted by blood against the walls of the arteries. SBP is the pressure inside the artery when the heart contracts and pumps blood through the body; while DBP is the pressure inside the artery when the heart is in resting and filling with blood.	Measure with a blood pressure monitor and a stethoscope.	Discrete quantitative	PAS: 120 – 139 mmHg PAD: 80 – 89 mmHg	Kolmogorov-Smirnov or U Mann U Whitney*
Diameter pupillary	The natural pupil of the human eye is usually approximately circular, for a given subject, the pattern of aberrations, diffraction, depth of field and retinal illumination depend on the pupil diameter, which in turn varies depending on the ambient lighting.	The pupillary diameter results from the balance between the sphincter muscle of the pupil and the radial fibers of the iris that have only innervation autonomous [11].	Quantitative continues	2 – 6 mm	Kolmogorov-Smirnov or U Mann's Whitney*
Conjunctival hyperemia	It is defined as the simplest reaction of the conjunctiva to a stimulus, a red appearance secondary to the vasodilation of the vessels is observed. the conjunctiva of variable intensity.	Direct observation. Classification by Efron scale (see Annex 9.2).	Qualitative ordinal	Degrees: 0= Normal 1= Very mild 2= Mild 3= Moderate 4= Severe	Pearson's X  or Exact of Fisher*
Changes in the AVMC	Spatial visual acuity is the ability to distinguish separate elements of an object and identify them as a whole. It is quantified as the minimum angle of separation (located at the nodal point of the eye) between two objects that allows them to be perceived as separate objects.	Snellen chart	Continuous quantitative	0.6 to 2.0	Kolmogorov-Smirnov or U Mann's Whitney*
Changes in Corneal and conjunctival TVL	Detection of epithelial defects in the cornea and conjunctiva.	Direct observation with slit lamp, it will be graded according to the SICCA (see Annex 9.3) [12].	Discrete quantitative	0 to 6	Kolmogorov-Smirnov or U Mann's Whitney*
Changes in Corneal and conjunctival TF	Detection of epithelial defects in the cornea and conjunctiva.	Direct observation with slit lamp, will be graded according to the SICCA (see Annex 9.3) [12].	Quantitative discreet	0 to 6	Kolmogorov-Smirnov or U

